## 4.5 Specimen Collection and HIV/STI Test Reporting

### 4.5.1 CBO specimen collection

Sites will use standard protocols for specimen collection for this study, as outlined in the Standard Operating Procedure guide for STI Specimen Collection and summarized below.

HIV testing (performed at follow-up appointments only) will be performed using the OraQuick rapid test. The test result should be recorded in the participant’s health record

[For BAC only] For syphilis serologic testing, the Research Coordinator will use the Syphilis Health Check™ Antibody Rapid Immunochromatographic Test from Diagnostics Direct. This test involves a finger prick blood draw, and the test takes 10 minutes to incubate before results are ready to be read. During this time, the Research Coordinator should have the participant collect his urine and rectal swab specimens. BAC visits with a phlebotomist will do syphilis testing via venipuncture as part of a full panel. In all cases, the participant’s syphilis test result will be recorded in their health record. Note: Participants who indicate a past syphilis infection will *not* be tested for syphilis at baseline or follow-up visits, except if doing a full panel at BAC with the phlebotomist.

STI testing supplies for Boom!Health will be ordered by PRIDE staff through Quest Diagnostics. BAC will order its own STI testing supplies through LabCorp.

CBO study staff will escort the participant to the participant restroom with the printed instructions on specimen collection and all labeled specimen collection devices and containers. They will instruct the participant where to place specimens when collection is completed, as well as where they can be found after completion of the specimen collection process, and will leave the participant to carry out the procedure in private. Once specimens are obtained, the study staff will ensure that urine and rectal swab samples are labeled correctly and will place them in the appropriate area in the laboratory designated for specimen pick-up.

BAC samples will be picked up and processed by LabCorp. Boom!Health samples will be picked up and processed by Quest Diagnostics. The Research Coordinators will track participants' STI results on RedCap and complete the Test Results Form on Qualtrics.

All positive HIV and STI test results will be conveyed to participants by CBO site staff using their standard protocols, and participants will be provided with access to treatment.

PRIDE will provide STI testing supplies to Boom!Health. CBO study staff may pick up the supplies from the PRIDE office, or PRIDE will deliver as-needed. STI test kit supplies include:

- Anal swabs
- Pee cups
- Beakers
- Test tubes (for urine and rectal swab samples)
- Syphilis Health Check™ kits (each with 20 test devices, 20 pipettes, and 5 ml diluent in a dropper bottle)
- OraQuick rapid tests

#### **4.5.2 Alternative means of specimen collection**

When participants move away or are otherwise unable to complete specimen collection at the clinic site, specimens may be collected via at-home testing or testing at central lab facilities (e.g. Quest Diagnostics). At-home testing kits may be mailed to a home address with instructions for use. YMHP research staff at PRIDE may be asked to ship kits to an alternate location deemed as a safe space, such as a youth center, and will require youth to speak with a trained PRIDE staff member to ensure these arrangements are both safe and allowable.

#### **4.5.3 HIV/STI Test Result Delivery**

All HIV and STI test results will be delivered following the CBOs' existing protocols for delivery of HIV/STI test results. Test results for participants who utilized at-home testing kits will be delivered following the corresponding PRIDE protocol for delivery of HIV or STI test results. Participants utilizing at-home testing kits determined to be HIV-positive at a follow up YMHP assessment will receive the results from a member of the PRIDE clinical team who is trained in HIV C&T, following the PRIDE protocol for delivering HIV positive test results. If a HIV/ STI test results in a positive test result, then a participant's results will be reported to State Health Departments in New York for surveillance purposes. Participants will be informed that their results will be shared with health departments in the site-specific consent form.

All participants who test positive for HIV will be referred for services, including referral for a confirmatory HIV test if needed. Similarly, all participants testing positive for an STI will be offered a referral for STI treatment.

#### **4.5.4 HIV/STI Test Reporting**

Upon receiving the test results from Quest/LabCorp, generally within 3 days, the CBO Research Coordinators will complete the Qualtrics STI Test Results reporting form for these and the rapid test results already recorded for that visit in the participant's CBO health record (HIV and syphilis).

Reporting to the NYCDOHMH will occur using existing standard protocols at each CBO, or by existing standardized protocols at PRIDE or the participant's testing provider for specimen collection done outside of the clinic setting.

#### **4.6 Incentives and Compensation**

For taking part in this study, participants will be paid for both the treatment sessions and assessments as follows, up to \$245 in gift cards if the participant completes the whole study:

Visit	Compensation amount
Baseline survey, STI and HIV testing, and YMHP Session 1 or eTAU session	\$50 in gift cards (\$25 gift card for completing the computer based survey and \$25 gift card for completing first YMHP or Treatment as Usual session, HIV and STI tests).
Program Sessions 2-4 (ONLY if randomized into YMHP)	MetroCard (\$5.50 value) and food voucher (\$7 value) for each of the three additional YMHP sessions. If the baseline and three additional YMHP sessions are complete participant will receive an additional \$20 gift card.
Post-test assessment (IP)	\$25 gift card (CASI-only assessment)
3-month assessment	\$50 in gift cards (\$25 gift card for completing the CASI plus \$25 gift card for completing HIV and STI testing).
6-month assessment	\$25 gift card (CASI-only assessment)
9-month assessment	\$50 in gift cards (\$25 gift card for completing the CASI plus \$25 gift card for completing HIV and STI testing).
12-month assessment	\$25 gift card (CASI-only assessment)
Optional Qualitative Interview	\$25 gift card (phone interview-only assessment)

#### 4.7 Criteria for Premature Discontinuation

Dropping participants simply means we have stopped following them but they remain enrolled. This is for two reasons: (1) Participants should not be dropped after randomization in any trial, in order to remain consistent with the guidelines for intention-to-treat (ITT) analyses; and (2) These situations reflect the reality of implementing an intervention in a real world setting and make meaningful data points in an effectiveness trial. The only legitimate reason to drop an individual from the total number of enrolled participants is if someone is found to be ineligible at the time of randomization. Anyone marked as “Withdrew from Study” for IRB purposes should be included in the IRB continuation, Data Safety Monitoring report, and the Research Performance Progress Report (RPPR).

Below are the categories of “dropping” participants along with their definitions. These categories should be accurately used in the site’s tracking materials if one of the conditions below occurs.

#### 4.8 Measures

All measures except HIV and STI Testing are administered at study assessments using a web-based CASI survey on an iPad at each site. See below for the CASI measures and schedule of measures by visit.

##### *Primary Outcomes*

- Substance Use/Abuse
  - ASSIST
  - PRIDE Grid
  - Cannabis Use – Perceptions of Criminality
- Sexual Risk Behavior
  - Main and Casual Partners
  - Harmonized Sexual Risk Behavior
- Pre-Exposure Prophylaxis (PrEP) Uptake
  - Motivational PrEP Cascade
  - General PrEP Experiences and Acceptability
  - Decisional Balance for PrEP Use
  - PrEP Treatment Adherence
  - Perceived Risk of HIV scale (only 2 questions)
  - The Contemplation Ladder: PrEP Use

##### *Other Self-Reported Measures*

- Demographics/Socioeconomic Characteristics
- Subjective Social Status
- Condoms during Anal Sex Contemplation Ladder
- Drug Use Contemplation Ladder
- STI Testing

- HIV Testing
- Patient Health Questionnaire for Anxiety and Depression (PHQ-8, GAD-7)
- Visual Analog Scale for Self-Efficacy of Five Outcome Behaviors
- Unmet Physical or Behavioral Health Care Needs
- ATN Social Support Measure
- Poor Family Management
- Parenting Style Questionnaire
- Comfort in Sexual Communication with Parents
- The Parent-Teen Sexual Risk Communication Scale
- Brief Perceived Ethnic Discrimination Questionnaire Community Version
- Group Membership Questionnaire
- Everyday Discrimination- Race and Ethnicity
- Everyday Discrimination- Sexual Orientation

*Client Evaluation of Intervention*

- Health-Care Climate Questionnaire
- Client Evaluation of Counseling
- Client Satisfaction Questionnaire

*Self-Management Measures*

- Behavior Rating Inventory of Executive Functions (BRIEF-A)
- Patient Activation Measure (PAM)

**See schedule of measures by visit on next page.**

	Brief CASI on iPad	Baseline	Immediate Post-Test	Follow-Up
Primary Outcomes	Substance Use/Abuse			
	ASSIST + PRIDE Grid	✓	✓	✓
	Cannabis Use Perceptions of Criminality	✓		
	Sexual Risk Behavior			
	Sexual Risk Behavior Main Partner	✓	✓	✓
	Sexual Risk Behavior Casual Partner	✓	✓	✓
	Harmonized Sexual Risk Behavior	✓	✓	✓
	Pre-exposure Prophylaxis (PrEP) uptake			
	Motivational PrEP Cascade	✓	✓	✓
	General PrEP Experiences & Acceptability	✓		✓
	Decisional Balance for PrEP Use	✓		✓
	PrEP Treatment Adherence		✓	✓
	Perceived Risk of HIV scale	✓	✓	✓
	The Contemplation Ladder: PrEP Use	✓	✓	✓
Other Self-Reported Measures	Demographics/Socioeconomic Characteristics	✓		
	Subjective Social Status Scale	✓		
	Condoms during Anal Sex Contemplation Ladder	✓	✓	✓
	Drug Use Contemplation Ladder	✓	✓	✓
	STI Testing (in past 3 months)	✓	✓	✓

S M M	HIV Testing		✓	✓
	Patient Health Questionnaire Anxiety and Depression (PHQ-8,GAD-7)	✓	✓	✓
	Visual Analog Scale for Self-Efficacy of Five Outcome Behaviors	✓	✓	✓
	Unmet Physical or Behavioral Health Care Needs	✓	✓	✓
	ATN Social Support Measure	✓		✓
	Poor Family Management	✓		
	Parenting Style Questionnaire	✓		
	Comfort in Sexual Communication with Parents	✓		
	The Parent-Teen Sexual Risk Communication Scale	✓		
	Brief Perceived Ethnic Discrimination Questionnaire Community Version	✓		
	Group Membership Questionnaire	✓		
	Everyday Discrimination- Race and Ethnicity	✓		
	Everyday Discrimination- Sexual Orientation	✓		
Client Evaluation	Client Evaluation of Counseling		✓	
	Client Satisfaction Questionnaire			✓
	Healthcare Climate Questionnaire		✓	
S M M	PAM	✓	✓	✓
	BRIEF-A	✓		

#### **4.8.1 Self-Management Model Measures**

The AC will develop and apply analytic approaches to assess the Five Components of Self-Management Model as a synergistic model within and across the *Scale It Up* projects, and how these components vary over time, are directly improved by interventions, and mediate intervention effects. Four components are considered predictive variables, and the AC will choose measures in collaboration with project leads and PRIDE PI. Sample measures, which were all used in the PIs' previous trials, include the Behavior Inventory of Executive Function for Problem Solving and Decision Making, Services and Support measure for Resource Utilization, and the Measures of Processes of Care for Provider Relationship. We hypothesize that these will predict the fifth component, patient self-management action.

## **5.0 INTERVENTION PROCEDURES**

### **5.1 Intervention Design and Procedures**

YMHP is a CDC Best Evidence Intervention [59] that utilizes MI and personalized feedback to reduce CAS and substance use among YMSM. The YMHP intervention will be delivered by MI-trained Health Educators employed at each of the two CBOs. Participants will be randomized to receive either the intervention or an eTAU session with the Health Educator. The intervention condition involves completion of 4 YMHP sessions and the delivery of PrEP information and navigation services to interested participants. The control condition involves the completion of a single session eTAU that reviews the array of services offered by the CBO and also provides an overview of PrEP and PrEP-related services.

#### **5.1.1 Four Sessions of YMHP**

##### ***Session One: Engagement; Focusing & Evoking on the First Target Behavior***

In Session 1, participants will choose which behavior to discuss first (sexual risk or substance use), and the Health Educator will elicit the client's view of the problem using standard MI techniques, building motivation for change by eliciting and reinforcing change talk and clarifying the youth's own personal priorities (through a structured values card sort activity). Basic information on PrEP efficacy will be provided using the ask-ask-tell-ask-reflect approach. The Health Educator will discuss options for a behavior change plan, and, if the client is willing to proceed, the client will set goals. The session ends with MI strategies to evoke the client's ideas about how to take steps towards change, consolidate their commitment to the plan, and problem-solving.

- Opening statement – Provide information as appropriate; set the stage for collaboration; introduce target behaviors
- Background and Priority Card Sort Activity – Use Open Questions and Reflections to understand what is truly important for each participant

- Ask permission to discuss the first target behavior; ask the client which one they would like to begin with and summarize participant's concerns
- Use strategies for eliciting change talk & managing discord
- At the end of the session, offer a closing summary highlighting any change talk or steps towards change; evoke commitment to attend future sessions

### ***Session Two: Second Target Behavior; Continue Focusing & Evoking***

Session 2 follows the same format as Session 1, but revolves around the second target behavior.

- Opening statement – highlight any change talk or plan from previous session; introduce second target behavior and collaborate on setting session agenda with client
- Briefly revisit last session's topic and check for any changes or recent events since you last met
- Ask permission to discuss second target behavior
- Use strategies for eliciting change talk and managing discord
- Offer a closing summary at the end of the session, highlighting change talk and any steps taken towards change

### ***Session Three: Consolidating Change Plan/Considering PrEP***

In Session 3, the Health Educator will review the change plan, continue to elicit and reinforce change talk, problem-solve barriers, consolidate commitment, and address maintenance of behavior change.

- Opening statement: Highlight and integrate change talk on both target behaviors and any ideas or goals the client has articulated around these behaviors; work collaboratively to set the agenda for the session
- Ask the client where they would like to go from here; or, ask permission to discuss collaborating on a change plan together
- Evoke client's ideas about change; build on past success; evoke and reinforce self-efficacy for taking steps towards change
- If appropriate, use the Ask-ask-tell-ask-reflect approach [60] for offering information or suggestions about PrEP education and work together on a navigation plan if appropriate; if offering suggestions be sure to reinforce client autonomy and offer a menu of options
- Collaborate with the client to build a change plan that reflects their goals, priorities and readiness to change; elicit the client's ideas about how the plan could be carried out, when the steps will occur – and why these changes are important; and how PrEP may or may not fit into change plans the participant has already made for their substance use and sexual health
- Offer a closing summary highlighting change talk and briefly reiterating the basic plan; reinforce client autonomy; remind the client that the next session will be focused on moving ahead independently (as it is the final YMHP session)

#### **Session Four: Consolidating Commitment; Relapse Prevention/Termination**

- Opening Statement: Summarize the plan developed previously and collaborate on setting the session agenda; introduce termination / last YMHP session;
- Check in on how the plan has been going since you last met; use strategies for evoking change talk / managing discord as appropriate; affirm client for any steps towards change;
- Evoke client's ideas about how to improve or adapt the plan; evoke and reinforce commitment for maintaining the plan moving forward
- Evoke client's ideas about what to do should problems arise in the future; develop a 'backup plan' as appropriate
- Summarize progress over the 4 sessions and address termination

### **5.2 Intervention Training and Supervision**

YMHP training will occur prior to the initiation of Phase 2, with ongoing coaching and supervision and training of new interventionists, as required. The interventionist training team consists of trainers from PRIDE's clinical team. The training procedure includes:

1. Initial 3-day training for Health Educators and their supervisors;
2. A 2-3 month training period of role-play practice, coding and feedback, and supervision modeling, including mock sessions with "standardized clients" role-played by PRIDE Research Assistants;
3. 1 hour weekly supervision sessions between the Health Educators and their supervisors;
4. Monthly supervision calls between supervisors and trainers from the PRIDE clinical team, including a quarterly Skype booster training (see *Booster Trainings* below); and
5. Ongoing quality assurance and feedback using MITI coding.

All materials (e.g., slides, training exercises, supervisory tools) will be packaged for potential dissemination. Any copyrighted media will be removed from these materials prior to dissemination.

#### **5.2.1 Initial and Pre-Trial Training**

The 3-day training will be held at PRIDE and follows a curriculum developed for our previous NIH-funded effectiveness trials. Health Educators and supervisors participate together. Days 1 and 2 include introductions to YMHP and MI, followed by an overview of how to deliver each of the 4 YMHP sessions. The full third day is dedicated to mocks, supervision, and introduction to the MITI. PRIDE will provide external MITI coding for the supervisor to use as feedback.

Following the in-person 3-day training workshop, all Health Educators and supervisors will each mock the intervention with a "standardized client" (played by a trained PRIDE RA) and submit the 4 roleplayed sessions to PRIDE. Then, supervisors will complete one supervision session with each Health Educator, with audio recordings uploaded into the study Dropbox. After each audio recording is uploaded to Dropbox, the Health Educator and supervisor will notify PRIDE

via the study email account. All mock sessions should be saved in the Dropbox sub-folder named “Pre-Trial.” All audio recordings uploaded to Dropbox will be downloaded to the PRIDE multimedia (M:) drive. They will be tracked in an Excel spreadsheet for MITI coding assignment. PRIDE will delete audio files from Dropbox monthly, and notify sites in advance via email each time.

The mock sessions will be MITI coded and PRIDE trainers will provide coaching and feedback. PRIDE trainers will use MITI thresholds for fidelity flagging. Those criteria include percent reflection, percent complex reflection, technical global, relational global, and MI non-adherent codes. For clearance, trainees should score in the “fair” range on all 5 elements by their final mock. If they are below in 1 or 2 domains, they will not have to redo the mock. However, by the 4th mock they should score at least “fair” to be cleared.

If there is staff turnover for any reason (e.g., staff leave the clinic, staff are unable to be cleared to see participants due to quality of delivery), then additional training will be provided to new staff members.

### **5.2.2 Booster Trainings**

The PRIDE Clinical Team will lead quarterly boosters via group Skype for supervisors. Prior to each quarterly booster, supervisors will submit a recording of a supervision session for review. Boosters will cover successes and challenges, MITI scores, updated MI Skill Development plans for each Health Educator, and role-plays of supervision skills. Someone from the PRIDE Clinical Team will join supervision sessions via Skype if MITI scores fall below competency without remediation. PRIDE will also lead annual in-person booster trainings covering MI skills and specific delivery of YMHP for supervisors and Health Educators.

### **5.2.3 Ongoing Monitoring and Supervision**

Once beginner competency is met, the supervisors will take over weekly individual supervision of the Health Educators. To prepare for these weekly meetings, supervisors are expected to listen to at least one session recording per week and review MITI coding when available. In cases of flagged sessions, supervisors are expected to review the MITI scores with the Health Educator and discuss ways to address fidelity concerns. If multiple sessions take place in the week of the meeting, the supervisors should work with the Health Educator to identify which session they would like to go over in the supervision meeting. If no sessions take place in the week of the meeting, the supervisor should use the meeting time to review and practice MI skills with the Health Educator, and/or review past sessions that were not discussed.

The MITI coding randomizer should flag for additional review any session where the Health Educator falls below “fair” on more than 2 domains. 10% of each Health Educator’s recordings will be randomly selected for MITI coding. These randomly coded sessions will be shared with the supervisors as a way to reinforce their internal barometers for “good enough” MI, rather than MITI only being used for comparing unsatisfactory delivery of MI. Ongoing fidelity issues may result in a Health Educator being required to attend additional training and/or removed from active session delivery until fidelity is achieved.

After reviewing a supervisee's session and before supervision, supervisors will complete the MI Coach Rating Scale ("Rating Form") via Qualtrics.

Each Health Educator will submit an electronic *Clinical Session Form* via Qualtrics upon completion of each non-mock YMHP session. PRIDE will notify the sites acknowledging the receipt of the *Clinical Session Form* or send a reminder to complete the form.

Supervisors will have monthly 30-minute supervision calls with trainers from the PRIDE Clinical Team to discuss ongoing implementation issues at their sites. Each monthly call will be audio recorded. If circumstances prevent a supervisor from attending a call, they are expected to review the recording. PRIDE staff will be available to answer questions as needed

## **6.0 DATA MANAGEMENT AND ANALYSIS PLAN**

### **6.1 Data Management and Data Quality**

PRIDE will be handling data management. Data will be entered directly by participants through Qualtrics. Data dictated by participants who request assistance completing surveys may also be entered by the Research Coordinators. The database, data structure, and data quality will be routinely reviewed by PRIDE. Where indicated, we will use full-information maximum likelihood estimation to account for missing data under Missing at Random (MAR) assumptions.

### **6.2 Quantitative Analysis Plan**

Primary Outcome Measures:

- Days of Illicit Drug Use (past 30 days)
- Days of Marijuana Use (past 30 days)
- Condomless Anal Sex Acts (past 30 days)

Secondary Outcome Measure:

- Days of Alcohol Use (past 30 days)

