#### **Phase 2**

Qualitative analysis: Interviews will be transcribed prior to data analysis. The team will use NVivo to conduct thematic content analyses to identify implementation barriers and facilitators. Using constant comparison analytic methods, a preliminary codebook will be developed both deductively and inductively. Research Scientist and another member of the team will code each interview. Divergent coding will be discussed, decision trails will be created at key decision-making junctures, and consensus-building strategies will resolve discrepancies. Findings will be used to inform revisions of the YMHP implementation package.

Statistical analysis: The primary hypothesis is that participants randomized to receive YMHP will demonstrate significant reductions in sexual risk behavior and associated health outcomes as well as substance use frequency and severity when compared to those who randomized to eTAU. We will utilize stratified block randomization with substance use and interventionist as the strata in order to assign all participants to a condition.

A series of bivariate analyses within SPSS (version 27) evaluated the success of randomization and the presence of differential attrition. With respect to randomization,  $\chi^2$  tests of independence evaluated between-condition differences across demographic characteristics (race and ethnicity, sexual identity, relationship status, education, income, and age). Where cell sizes for categorical variables were too small ( $n < 5$ ) to permit chi-square tests, we utilized a Fisher's exact test. The generalized linear model function in SPSS – which permits the specification of Poisson and negative binomial outcome variable distributions – was used to evaluate between group differences in baseline frequency of primary (marijuana use days, other illicit drug use instances, and CAS with male partners) and secondary (alcohol use days) outcomes. Likewise,  $\chi^2$  analyses were used to evaluate whether the probability of retention at each follow-up was associated with site, condition or categorical demographic factors; meanwhile, the generalized linear model component of SPSS was used to test whether retention at follow-up was associated with baseline primary or secondary outcome frequency.

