Outcome analyses were conducted using piece-wise latent growth curve (LGC) models following procedures outlined by Chou et al., (Chou et al., 2010) and used previously in similar studies (Flora, 2008; Kohli et al., 2013; Li et al., 2001; Naar-King et al., 2009; Naar et al., 2020). Growth trajectories over-time following the delivery of an intervention may be characterized by a large initial response followed by a more sustained trajectory with a less dramatic slope. Piece-wise LGC models quantify this kind of trajectory through the use of two slopes. Slope 1 quantifies the change from baseline to the immediate post-test (3-month follow-up). Meanwhile, Slope 2 quantifies the trajectory over the post-intervention follow-up period.

All primary (marijuana use, other illicit drug use, and CAS with male partners) and secondary (alcohol use) outcomes were modeled as negative binomial distributions. All models were estimated using full-information maximum likelihood estimation in MPlus Version 8.0. This permitted the retention of all randomized cases consistent with a true intent to treat paradigm. Many commonly used indices of model fit are not available for growth models with count-distributed outcomes (i.e., root-mean square error of approximation (RMSEA)  $\leq 0.05$ , Tucker-Lewis fit index (TLI)  $> 0.95$ , and comparative fit index (CFI)  $> 0.95$ ). Model fit was therefore

evaluated using a robust log-likelihood  $\chi^2$  test (Satorra & Bentler, 2001) comparing the log-likelihood of the specified model to a null-model – in which all structural coefficients associated with the regression of latent growth factors on condition and site were constrained to be zero.

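### Section 6.2 gives the primary illicit-drug outcome as days in the outcome list and as instances in the analysis text, and the growth-model paragraph gives no unit to settle it

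*Combined protocol and SAP*

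**What the plan says.** Section 6.2 describes the primary outcomes in three places.

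- **Outcome list, at the head of 6.2.** The drug outcome is "Days of Illicit Drug Use (past 30 days"). Beside it stand "Days of Marijuana Use (past 30 days") and "Condomless Anal Sex Acts (past 30 days").
- **Phase 2 statistical analysis, baseline comparison.** The outcomes compared between arms at baseline are "primary (marijuana use days, other illicit drug use instances, and CAS with male partners"). Alcohol, the secondary outcome, is in days.
- **Phase 2 statistical analysis, growth-model paragraph.** The outcomes modelled are "All primary (marijuana use, other illicit drug use, and CAS with male partners") plus alcohol use. The paragraph adds that these "outcomes were modeled as negative binomial distributions". No unit or recall window is given for any of them.

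Section 4.8 also has a list headed as primary outcomes, but it names instruments (for drugs, the ASSIST and the PRIDE Grid) and gives no scoring rule.

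**The concern.** A primary outcome needs one unit, one scope and one window. Here the drug outcome has two units within one section. This does not look like loose shorthand: the sentence that speaks of instances keeps days for marijuana and for alcohol, and changes the unit only for the other drugs. The scope also moves, from illicit drugs in the list to other illicit drugs in the analysis text.

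A reader therefore cannot tell from the plan which variable the primary drug test uses. The two versions can give different answers, and the plan does not say in advance which one counts.

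**Working it through.** **1. The drug outcome, place by place.**

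| Place in 6.2 | Unit | Drugs covered | Window |
|---|---|---|---|
| Outcome list | days | illicit drugs; marijuana listed separately | past 30 days |
| Baseline comparison | instances | other than marijuana, apparently | not stated |
| Growth-model paragraph | not stated | other than marijuana, apparently | not stated |

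The first two rows conflict on the unit. The third row, which governs the test, agrees with either.

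**2. Does the distribution settle it?** No. Days and instances are both counts, and a negative binomial can be fitted to either.

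**3. Does the power analysis settle it?** Section 6.2.4 treats substance use as a proportion, 0.80 against 0.62, with 83.0% power at 221 retained (260 × 0.85). With n = 221/2 = 110.5 per arm, two-sided alpha 0.05 (sidedness is not stated), and the counselor effect left out because no variance is given:

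- Formula: power = Φ{[|p1 − p2| − 1.96 √(2 p̄(1 − p̄)/n)] / √([p1(1 − p1) + p2(1 − p2)]/n)}, with p̄ = (0.80 + 0.62)/2 = 0.71.
- Null term: 1.96 × √(2 × 0.71 × 0.29/110.5) = 1.96 × 0.0610 = 0.1197.
- Denominator: √((0.1600 + 0.2356)/110.5) = 0.0598.
- Power = Φ((0.18 − 0.1197)/0.0598) = Φ(1.01) = 84.3%, within 2 points of the stated 83.0%.

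The figure reproduces, but it is no help here. For the same drugs and window, days are zero exactly when instances are zero, so any-use proportions are the same in both units.

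**4. How far apart can the two variables be?** Take a hypothetical participant who uses two drugs, neither of them marijuana, twice each on the same 5 days.

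- Days with any use: 5.
- Days summed over drugs: 2 × 5 = 10.
- Separate uses: 2 × 2 × 5 = 20.

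The plan does not define an instance, so it could mean the second or the third. Days with any use cannot exceed 30. Days summed over k drugs can reach 30 × k, and separate uses have no fixed ceiling.

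**5. Can the treatment ratio differ?** Suppose this participant then uses each drug once, not twice, on the same 5 days. Separate uses fall to 2 × 1 × 5 = 10, a ratio of 10/20 = 0.5. Days stay at 5, a ratio of 5/5 = 1.0. The example is constructed, and shows only that the unit can change the effect measured.

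**6. Error rate if a choice were made after the fact.** Let z1 and z2 be the tests of the two versions, bivariate normal under the null with correlation ρ. The chance that at least one exceeds 1.96 in absolute value is 1 − P(|z1| ≤ 1.96 and |z2| ≤ 1.96):

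| ρ (assumed) | Error rate |
|---|---|
| 0.6 | 8.8% |
| 0.8 | 7.8% |
| 0.9 | 7.0% |

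The documents give no correlation between the versions, so the range is an assumption.

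**7. The CAS outcome.** The list counts acts in the past 30 days and does not state the partners' sex. The analysis text adds male partners and drops the unit and the window. An act count limited to male partners fits all three places, so this is incomplete wording and not a shown conflict.

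**The case against.** The strongest reply is that the list is the only place set out as the definition of the outcome measures. The conflicting unit occurs once, in a sentence about baseline balance, and the growth-model paragraph does not contradict the list. On that view a loose word in a balance check leaves the tested outcome alone. Part of this stands: a reader might infer that the outcome model itself is stated in instances, and it is not. But the baseline sentence labels its variables as the primary outcomes, and the growth-model paragraph repeats its drug and CAS wording, "marijuana use, other illicit drug use, and CAS with male partners", and not that of the list. With no unit there, the conflict stays open.

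Four stronger readings are tempting and should not be drawn.

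- **That two of the three primary outcomes are contradictory.** The list never says that CAS covers partners of any sex. Section 3.1 requires recent sex with men, so the male-partner wording may only spell out the intended scope. It could change values for participants who also have other partners, but no different outcome is shown.
- **That the marijuana and illicit-drug outcomes overlap.** The list gives marijuana its own line, the analysis text speaks of other illicit drugs, and Section 4.1.4 stratifies marijuana-only use against other substance use. All of this keeps marijuana separate. The list could say so outright, but overlap is unlikely.
- **That the result was picked from several versions.** Nothing in the documents shows that both versions were tested.
- **That either version can be derived from data already held.** The items of the drug-use grid are not shown. If days are recorded per drug, days with any use cannot be recovered exactly when drugs share days.

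**Conclusion.** The point holds for the illicit-drug outcome, one of three listed primary outcomes. Section 6.2 gives it in days in one place and in instances in another, and no section reconciles them. The two can differ severalfold for one participant (5 against 10 or 20 in the example, depending on what an instance means) and can give different rate ratios. The effect on this trial's estimate cannot be computed from the documents.

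The error rate of about 7% to 9% is illustrative. It rests on an assumed correlation of 0.6 to 0.9 and on reporting the better of two versions. The power figures are not in question. The CAS wording is a smaller clarification.

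The Phase 2 statistical text is in the past tense and the analysis plan was last updated on 10.1.2021. If the analysis had already been run by then, choosing a definition afterwards would not restore pre-specification. Disclosure of the version analysed is therefore as important as the wording.

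**What to change.** 1. Use one definition of the drug outcome in the outcome list, the baseline comparison and the growth-model paragraph. The listed one is the natural default: the number of the past 30 days with use of any illicit drug other than marijuana, range 0 to 30.
2. Name the source instrument. If the grid records each drug separately, state how days are combined across drugs.
3. State which version was analysed. Report any other version, including an instance count, as secondary and as a departure from the list.
4. For CAS, use the same words throughout: the number of condomless anal sex acts with male partners in the past 30 days.

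The cost is a few lines of plan text and, at most, re-deriving and re-running one outcome. Whether the collected items support a count of days with any drug has to be checked against the grid. If they do not, the plan should say so and define the nearest variable that they do support.
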